Perception of medication will be evaluated using Portuguese general BMQ, the willingness to be deprescribed will be assessed with two open-questions (one to assess the facilitators and the other to assess the barriers), and the actual self-medication will be evaluated with an analogic visual scale (0 to 10) about the need to self-medicate and its justification.

For those not knowing how to write or read, someone of their knowledge, will fill in the open questions, with their answers.

In case of less than 5% of answers of the open questions, two patient groups will be invited to make a focus group asserting reasons for accepting deprescribing.

Phase III: impact of enablement of older adults in their willingness to deprescribe and quality of life

Design

Non-pharmacological randomised clinical study, intended to last for six months.

Setting

Primary Care Centres in Portugal will be randomly selected from six Health Centres of Centre of Portugal (Aveiro, Castelo Branco, Coimbra, Guarda, Leiria and Viseu)

Sample size

Will be created two groups with a minimum of 190 patients each (one will be the intervention group and the other the control).

Study procedures

This phase of the study is expected to start in September 2019 and will last for 6 months.

Again, GPs sampling will be made according to existing files and those who accept to participate will recruit their own patients. Patients from previous phases can be enrolled in phase III. Assuming that a GP will be able to include at least 6 patients, a total of 64 GPs has to be enrolled in the study. Enrolled GPs will be instructed to invite all older adult (≥ 65 years) patients attending to the primary care consultation to participate in the study during until obtaining the sample size and being randomized according to the table for study entry. The geographical areas of work, the Districts, will be randomized for entry into exposed and unexposed groups. Those patients willing to participate in the study must give written informed consent and present willingness and ability to comply with the study requirements.

Exclusion criteria: Being acutely unwell in the last three weeks, and refuse to participate.

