Two groups will be created with a minimum of 190 patients each, one of which will be composed from patients from the region of Aveiro, Coimbra and Guarda and the other from patients from the region of Castelo Branco, Leiria and Viseu. In the intervention group we will give enablement tools and talks with their GPs about how to issue the problem of polypharmacy. The information given in this group will result from the knowledge obtained in phase II in the shape of small leaflets and other information materials to be made according to the best practice, to be given and remembered at scheduled times to the intervention group.

Data collection

The collection of the data will occur in the beginning and end of phase II.

Patient's socio-demographic and clinical characteristics and medication will be registered using the same methodology as described in phase I.

Perception of medication will be evaluated using Portuguese general BMQ, the willingness to be deprescribed will be assessed with two open-questions (the same as phase II), and the quality of life we will assessed with EQ-5D.

For those not knowing how to write, someone of their knowledge, will fill in the open questions.

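### Phase III allocates whole districts and has GPs recruit their own patients, but does not withhold the district's arm until consent and baseline are complete

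*Protocol*

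**What the plan says.** All of the following is in the Protocol, section 4, Phase III, unless another place is named.

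- **Who recruits.** GPs are approached from existing files, and "those who accept to participate will recruit their own patients".
- **Whom they invite.** "Enrolled GPs will be instructed to invite all older adult (≥ 65 years) patients attending to the primary care consultation", with no fixed days or weeks. Invitation continues "until obtaining the sample size and being randomized according to the table for study entry".
- **What is allocated.** "The geographical areas of work, the Districts, will be randomized for entry into exposed and unexposed groups".
- **How the groups are made up.** One group consists of "patients from the region of Aveiro, Coimbra and Guarda and the other from patients from the region of Castelo Branco, Leiria and Viseu". Which of the two receives the intervention is not stated.
- **What the intervention is.** "In the intervention group we will give enablement tools and talks with their GPs about how to issue the problem of polypharmacy". Section 6 repeats this.
- **What patients are told.** Under section 9.1.1.1 the consent form describes the intervention in detail, and consent must be documented before the intervention starts.
- **Who knows the participants.** Under section 9.1.2 only the GP knows who is being studied.
- **The primary outcome.** Willingness to be deprescribed (sections 1.1 and 3), assessed with two open questions (section 7.1).

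**The concern.** When whole districts are allocated, a GP who knows the district's arm knows the arm of every patient he or she is about to invite. Patients may know it too. Three things can then differ between arms for reasons unrelated to the intervention's effect: whom the GP invites, who agrees, and how those who agree answer the baseline questions.

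The primary outcome makes this more than a formality. Willingness to be deprescribed is an attitude, and the same attitude plausibly influences whether an older person is approached about, or accepts, a study on reducing medicines. Selection would therefore act on the outcome itself. The district draw does not protect against it, because the selection happens after the units are formed. A larger sample does not help either, because this is bias and not sampling error.

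**Working it through.** **1. The plan's own figures.** Section 8.2 gives 380 patients from a 95% confidence interval and a 5% maximum error. With p = 0.5 (my assumption; the protocol gives no p), n = 1.96² × 0.5 × 0.5 / 0.05² = 384.16, which rounds up to 385. The stated 380 is 5/385 = 1.3% lower. It gives 380/2 = 190 per group and 380/6 = 63.3, so 64 GPs, as stated. The point made here does not depend on these figures. They show only that each GP needs about 380/64 = 5.9 patients before recruitment can stop.

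**2. What a GP can know.** If any three of the six districts could be drawn into one group, there are C(6,3) = 20 allocations. If the two named groups were fixed before the draw, there are 2. The protocol does not say which applies. For a GP's own patients it makes no difference, because under either reading they are all in one arm.

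**3. When the GP can know it.** The text permits three sequences:

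| Release of the district's arm | Consequence |
|---|---|
| Before recruitment | Every invitation, acceptance and baseline answer can be made with the arm known |
| During recruitment | The same holds for all later invitees in that district, and in all six districts if the two groups were fixed beforehand |
| After consent and baseline are complete | No exposure |

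Only the third sequence protects the comparison, and no sentence requires it. The data collection paragraph for Phase III places collection at the beginning and end of a phase that it labels II. It does not order baseline relative to allocation.

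**4. The wording on randomisation.** One sentence speaks of patients being randomised according to a table. The next says that districts are randomised. If the district decides the arm, a patient-level table has nothing left to allocate. The table is not described, so it cannot be relied on as a concealment step.

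**5. How far the invite-all instruction reaches.**

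| Route to bias | Does the instruction cover it? |
|---|---|
| Selective invitation | In part. In Phases I and II the GP works on five set days over three weeks; Phase III replaces this with an open period that ends at a target number |
| Checking that all were invited | No. No log of eligible, invited or refusing patients is described, and only the GP knows who is studied |
| Selective refusal | No. Patients read about the intervention before deciding |
| Baseline answers given with the arm known | No |

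**6. Size.** A numerical bias needs a defined endpoint and a selection rate. The protocol gives two open questions without a scale, coding or proportion, and no figures on invitation or refusal. No size follows from it.

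**The case against.** The strongest reply is that the protocol already tells GPs to invite every older attender, so choosing patients by their interest in stopping medicines would breach a written instruction. That is right as far as it goes: the instruction is a real safeguard. What it leaves open is refusal, baseline answers, and any means of verifying that it was followed.

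Second, the phrase about reaching the sample size and being randomised can be read as recruitment first and allocation afterwards, which is the safe sequence. That reading is possible. It is not stated, and the same phrase describes patient-level randomisation that the next sentence contradicts. The schema in section 1.2 could not be read in the text available and might settle the order.

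Third, each patient must consent before any study procedure (section 9.1.1.2). This orders events within a patient. It does not stop the district's arm from being known when that patient is approached.

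Fourth, section 8.3 allows ANCOVA. The adjustment is optional. It cannot recover people who were not invited or who declined, and it relies on baseline answers that may themselves have been given with the arm known.

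Finally, a shared arm within a district is a feature of any cluster design and is not a flaw in itself. That is accepted; the gap lies in the order of recruitment and disclosure, which is a matter of trial conduct and belongs in the protocol.

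**Conclusion.** The point holds in a limited form. As written, Phase III combines recruitment by the GP, district-level allocation and an intervention that involves the same GP, and it contains no step that withholds the arm until consent and baseline are complete. Recruitment bias in the primary outcome is therefore possible and not prevented. The correction is cheap and should be made. The conclusion rests on the readable text alone.

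Three stronger readings are not supported:

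- A reader might infer that GPs will know the arm in advance. The protocol does not say when the draw is made or released, so this is possible but not documented.
- A reader might infer from the two named groups that only two allocations were ever possible. The names might equally report the result of a draw among the six districts.
- A reader might attach a size: with 190 per group the 95% margin for a difference between two proportions near 0.5 is 1.96 × √(2 × 0.25/190) = 10.05 points, so an assumed shift of 5 to 10 points would be about half to all of it. The arithmetic is correct, but the shift has no basis in the documents, the protocol defines no binary willingness endpoint, and the comparison assumes that a baseline imbalance carries over in full to the result and ignores clustering. It should not be cited as the size of the bias.

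**What to change.** Make three changes to the Phase III study procedures.

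1. State that consent and baseline data are completed in all six districts before the district allocation is drawn, or before it is released to GPs and patients. It should be all six because, if the two groups are fixed, releasing one district's arm discloses the others.
2. Reconcile the sentence about the table for study entry with the sentence that randomises districts, so that one unit and one procedure of allocation remain.
3. Have each GP keep a log of eligible, invited and refusing patients, and report the counts by arm. This adds a check on the existing invite-all instruction and does not replace it. The log can hold counts only, which respects the rule that only the GP knows who is studied.

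The cost is mainly calendar time. Phase III is planned to last 6 months (section 4) and each participant takes part for 6 months (section 1.1), which leaves 6 − 6 = 0 months for recruitment. Under the new sequence the intervention starts only after baseline closes, and patients enrolled early must wait. The Phase III calendar therefore needs a stated recruitment period before the six-month follow-up. The length of that period cannot be derived from the documents. The log is a single form per GP, and the sample size, outcomes and intervention do not change.

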1 PROTOCOL SUMMARY

1.1 SYNOPSIS

Title:	Deprescribing: a portrait and out-comes of the reduction of Polypharmacy in Portugal (DePil17-20)
Study Description:	This study protocol comprises three phases. The first two phases will be nationwide and aim to evaluate the prevalence and patterns of polypharmacy and assess the barriers and facilitators of deprescribing perceived by older adults, as well as their willingness to be deprescribed and to self-medicate. The third and last phase will be a non-pharmacological randomised clinical study to measure the impact of enablement of older adults in their willingness to be deprescribed and related quality of life.
Objectives:	Primary Objective: Willingness to be deprescribed after the intervention Secondary Objectives: Quality of life after the intervention
Study Population:	Older adults (≥ 65 years) in Portugal
Description of Study	In the intervention group the investigators will give enablement tools and talks with their General Practitioners about how to issue the problem of polypharmacy.
Intervention:	
Study Duration:	36 months.
Participant Duration:	6 month.

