1.2 SCHEMA

2 INTRODUCTION

Polypharmacy is defined as the simultaneous taking of five or more drugs. It's present in 30-70% of older adults (1) and it's a significant predictor of the risk of falls (2) and other iatrogenic complications (3), inappropriate prescriptions (4), reduced patient's adherence (5), drug interactions (6), hospital admissions (7) and mortality (8). It is estimated that at least 75% of this adverse event is potentially preventable (9).

It is necessary to distinguish between appropriate and inappropriate medications (10), because as people get older the benefit/risk ratio of medications changes meaning that medications that were once appropriately prescribed may have become inappropriate (11). Potentially Inappropriate Medications (PIMs) are those for which the harms outweigh the benefits (12). Available data indicate that 20 to 65% of older adults are taking at least one PIM, leading to a high risk of adverse drug reactions, morbidity and mortality (13). There is a lot of information available to guide prescribers to start and maintain drug therapies that are safe and effective, but there is lack of knowledge concerning its reduction and/or withdrawal so maintaining safety and effectiveness (3, 8).

Deprescribing can be defined as the withdrawal of PIMs, under medical supervision, with the objective of managing the polypharmacy and improving health outcomes (14). However, it isn't risk's deprived, it can cause abstinence syndrome, rebound effects, pharmacokinetic/pharmacodynamic changes in the metabolism of not interrupted drugs and recurrence of symptoms that were in treatment by the withdrawn drug (1, 2).

So the decision to deprescribe results from a careful weighting between the therapeutic objectives and the risk/benefit ratio (15, 16).

Several deprescribing processes have been proposed in the literature (2, 17) and involve revision of all actual medications, identification of inappropriate medications (considering harms and benefits of medication use in the individual and in the setting of life expectancy and care goals), prioritisation of medications for withdrawal, withdrawal of medications (often with tapering) and close monitoring and support and also with documentation of the improvement in health and quality of life and the reduction of adverse effects (18).

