5 STUDY POPULATION

Older adult (≥65 years) patients attending to the primary care consultation in Portugal.

Exclusion criteria: Being acutely unwell in the last three weeks, and refuse to participate.

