6 STUDY INTERVENTION

In the intervention group we will give enablement tools and talks with their GPs about how to issue the problem of polypharmacy.

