7 STUDY ASSESSMENTS AND PROCEDURES

7.1 EFFICACY ASSESSMENTS

List and description of the procedures/evaluations to be used:

- Portuguese Beliefs about Medicines Questionnaire
 - For evaluation of the perception of medication
- EuroQol Five Dimensions Questionnaire
 - For assessment of the quality of life
- Two open-questions (one to assess the facilitators and the other to assess the barriers)
 - For assessment of the willingness to be deprescribed

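### Phase III has no medication criterion, so patients taking no medicine can enter a trial whose primary outcome is willingness to be deprescribed

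*Protocol*

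**What the plan says.** **Who can enter.** In section 4 (Phase III, Study procedures) GPs are told to "invite all older adult (≥ 65 years) patients attending to the primary care consultation". Section 5 gives the study population as "Older adult (≥65 years) patients attending to the primary care consultation in Portugal", followed by "Exclusion criteria: Being acutely unwell in the last three weeks, and refuse to participate". The synopsis also defines the population by age alone. Participants must be willing and able to comply with study requirements, but that is not a medication criterion.

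**What is measured.** The synopsis states "Primary Objective: Willingness to be deprescribed after the intervention". Section 7.1 lists two open questions, one on facilitators and one on barriers, "For assessment of the willingness to be deprescribed". The document does not give their wording. Section 3 words the primary objective in terms of older adults who are being deprescribed.

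**What deprescribing and the intervention are.** Section 2 says: "Deprescribing can be defined as the withdrawal of PIMs, under medical supervision, with the objective of managing the polypharmacy". Section 6 describes the intervention as enablement tools and "talks with their GPs about how to issue the problem of polypharmacy".

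**What is recorded.** For Phase III, "clinical characteristics and medication will be registered using the same methodology as described in phase I". The phase list in section 4 shows that this includes the number of drugs and their active component. The information is collected as data and is not used for entry.

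**Phase II.** The phase heading refers to adult patients with polypharmacy. The Phase II procedures invite all attenders aged 65 or over, and item 2 of the phase list speaks of older adults.

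**The concern.** Willingness to be deprescribed is a question about a patient's own medicines. For someone taking none, it has no object. The two open questions may draw out a general view, but it would be a view about a situation the patient is not in. The intervention, aimed at the problem of polypharmacy, also has little to act on in that patient.

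Two things are at stake. First, the primary outcome means something different for these patients than for the rest, whatever their number. Second, if they respond less to the intervention than others do, the average difference between groups shrinks while the sample size stays the same. Eligibility is fixed in the protocol, so this is not a matter that can be left to a statistical analysis plan.

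The Phase II discrepancy is separate and smaller: one phase has its population described in two ways.

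**Working it through.** **1. The eligibility text.** The synopsis, the Phase III procedures and section 5 contain one age limit, attendance at a consultation, and two exclusions. None mentions a number of drugs, polypharmacy or a potentially inappropriate medication (PIM). A patient on no medicine therefore meets every stated criterion.

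**2. The plan's own sample size.** Section 8.2 gives 380 patients from a 95% confidence interval and 5% precision; section 4 gives 190 per group. The single-proportion formula with p = 0.5 (assumed worst case) is

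n = 1.96² × 0.5 × 0.5 / 0.05² = 384.1, rounded up to 385.

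This is the Phase I and II figure. The Phase III figure of 380 is close to it and would follow exactly from a finite population correction with about 35,100 people, a number the protocol does not give. The calculation contains no effect size and no power, so any statement about power needs assumptions from outside the document.

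**3. Illustration of dilution.** Inputs from the protocol: 190 per group; two-sided 0.05 (section 8.3). Assumptions: the outcome is treated as a proportion; the control rate is 50%; the effect in patients on medicine is 14.2 points, chosen because it gives 80% power; patients on no medicine do not respond; there is no clustering. With a share s on no medicine, the effect is d = 14.2 × (1 − s), and

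power = Φ[(d − 1.96 × SE₀) / SE₁],

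where SE₀ uses the pooled proportion and SE₁ the two separate proportions. At s = 0, SE₀ = 0.0508 and SE₁ = 0.0503, so power = Φ[(0.142 − 1.96 × 0.0508) / 0.0503] = Φ(0.845) = 80%.

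| Share on no medicine | Number among 380 | Diluted effect (points) | Power |
|---|---|---|---|
| 0% | 0 | 14.2 | 80% |
| 2% | about 8 | 13.9 | 78% |
| 5% | 19 | 13.5 | 76% |
| 10% | 38 | 12.8 | 71% |
| 20% | 76 | 11.4 | 61% |

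With the effect reset to give 80% power at a control rate of 30% (13.8 points), the diluted figures are 78%, 76%, 72% and 62% (61.4% before rounding up, so 61% to 62%). At a control rate of 70% (12.2 points) they are 78%, 75%, 70% and 59%. The choice of control rate moves the result by about 1 point.

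**4. Clustering.** Districts are randomised, three per group, so the unclustered figures are not the trial's actual power. With an assumed district intraclass correlation of 0.01, the design effect is 1 + (190/3 − 1) × 0.01 = 1.62 and the effective size is 190 / 1.62 = 117 per group. With only six districts, a t reference on 4 degrees of freedom is needed. It gives about 40% power before any dilution. Clustering is thus the larger problem, and the table shows only the relative effect of dilution.

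**5. Cost of the criterion in screening.** Attenders needed for 380 patients = 380 / (1 − s): 388, 400, 422 and 475 for shares of 2%, 5%, 10% and 20%.

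**6. If patients are left out of the analysis instead.** The group size becomes 190 × (1 − s) = 186, 180.5, 171 and 152, with the full 14.2-point effect. Power is 79%, 78%, 76% and 71%, again unclustered.

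**The case against.** **The broad population is deliberate.** Older adults are named consistently in the synopsis, the objectives, the Phase III text and section 5. This stands. The point does not dispute the broad population; it asks only for the minimum that the outcome needs.

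**Patients on no medicine may still respond.** The outcome comes from open questions and the intervention is leaflets and talks, so a stated attitude could shift without a current medicine. This stands in part. A reader might infer that these patients can only dilute the comparison, but the document does not establish that: zero response is an assumption, and dilution is likely rather than certain.

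**The definition in section 2 points further than one medicine.** It speaks of withdrawing PIMs to manage polypharmacy, so a patient on one appropriate drug has nothing to withdraw either. A reader might conclude that Phase III should be confined to patients with polypharmacy or a PIM, and might add weight by applying the protocol's 30–70% polypharmacy prevalence to the sample. The documents do not support that step. No section sets such a threshold for Phase III, and patients below the polypharmacy threshold still have medicines about which willingness can be asked. They are a different subgroup, so that prevalence is no measure of the loss described here.

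**The loss is small and built on assumptions.** This stands. The effect, control rate and share are all assumed, no binary willingness endpoint is defined, and at shares of 2–5% the loss is 2 to 4 points.

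**The Phase II heading is editorial.** This stands too, and it adds nothing to the weight of the Phase III point.

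**Conclusion.** The point holds in a limited form. Phase III admits patients taking no medicine although its primary outcome presupposes one. These patients can at most state a hypothetical attitude and are likely to weaken the comparison. Their share is not given and may be small.

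On the stated assumptions the loss of power is 2 to 4 points at shares of 2–5%, 9 points at 10% and 19 points at 20%. These figures rest on a back-solved effect, an assumed control rate, no response in these patients and no clustering. They show scale and are not an estimate for this trial. The loss at small shares is well below that from randomising six districts.

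This does not invalidate the trial. It is worth correcting because the remedy is a single line and makes the primary outcome meaningful for every participant.

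**What to change.** 1. Add to section 5 and to the Phase III procedures: *Phase III: currently taking at least one medicine*. Confine the line to Phase III. Section 5 is not phase-specific, and Phase I needs all attenders as the denominator for polypharmacy prevalence. The line does not restrict entry to patients with polypharmacy or a PIM.
2. If recruitment has begun, make the willingness comparison in patients with at least one drug recorded at Phase III baseline, by the same rule in both groups. Report the number left out per group. Show quality of life both in all patients and in this same set, so that the two outcomes can be read on one population.
3. Step 2 needs medication recorded at the start of Phase III. The Phase III data collection paragraph places collection at the beginning and end of phase II, so that timing must be reconciled.
4. Editorial: make the Phase II heading and procedures name the same population. The smallest edit is to change the heading to older adults, as in the procedures and the phase list.

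**Cost.** One eligibility line and one heading edit; GPs already record the number of drugs. Screening rises to between 388 and 475 attenders for 380 patients if 2–20% take no medicine (an assumption). Results would no longer speak for attenders on no medicine. The fallback in step 2 instead leaves about 186 to 152 patients per group over the same range of shares.

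### Phase III gives allocation statements that do not fit together, and any reading that keeps the named district groups places whole districts, three per arm, inside one arm

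*Protocol*

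**What the plan says.** All statements are in Protocol section 4, Phase III.

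- **Label.** The design is given as "Non-pharmacological randomised clinical study, intended to last for six months".
- **Patients.** GPs invite their older patients until the sample size is reached, the patients "being randomized according to the table for study entry". What the table lists is not described.
- **Districts.** The next sentence says: "The geographical areas of work, the Districts, will be randomized for entry into exposed and unexposed groups".
- **Named groups.** The following paragraph forms two groups. The first is described as "one of which will be composed from patients from the region of Aveiro, Coimbra and Guarda". For the second, the protocol names the three remaining districts: "the other from patients from the region of Castelo Branco, Leiria and Viseu". It does not say how these sets were formed or which one receives the intervention.
- **Size.** The setting is "six Health Centres of Centre of Portugal (Aveiro, Castelo Branco, Coimbra, Guarda, Leiria and Viseu"). Each group has at least 190 patients, and 64 GPs are to include at least six patients each.

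Section 8.3 sets a two-sided 0.05 level, names χ², ANOVA or Kruskal-Wallis for group comparisons, and allows ANCOVA for confounding factors that it does not name.

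**The concern.** If a whole district belongs to one arm, a patient-level table has nothing left to allocate. If a patient-level table allocates, the arms cannot consist of separate districts. If the two sets are fixed beforehand, the six districts are not being randomised one against another. A site that follows one sentence departs from another.

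The arm comparison serves the primary objective, willingness to be deprescribed. When districts are nested in arms, any lasting difference between the two sets (schooling, access, prescribing habits) enters the contrast together with the intervention effect. Recruiting more patients in the same six districts does not shrink that part. How far the word 'randomised' can support a causal reading therefore depends on how the two sets arose, and the protocol does not say.

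**Working it through.** **1. The plan's own size.** Section 8.2 asks for 380 patients from a 95% interval with 5% precision. The single-proportion formula gives 1.96² × 0.25 / 0.05² = 384.1, so 385; 380 is close to this. The GP count agrees: 64 × 6 = 384. The calculation contains no term for districts or GPs.

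**2. Which statements can coexist.**

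| Pair | Compatible? |
|---|---|
| Patient table and district randomisation | Not if the table lists patients; yes if it is only the list of districts |
| Patient table and named groups | Not if the table lists patients |
| District randomisation and named groups | Only if one toss decides which set is exposed, or the sets result from a draw already made |

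The protocol confirms neither condition in the last row. It puts the district randomisation in the future tense, although the sets are already named.

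**3. Number of possible allocations.**
- Free draw of 3 of 6 districts: C(6,3) = 20.
- Two preset sets, one toss: 2.
- Preset sets with the exposed set also fixed: 1, which is no randomisation.

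**4. Size of the confounding and its effect on precision.** The protocol gives no intraclass correlation (ICC), so these are assumptions: binary outcome near 50% (total variance 0.25), end-of-study data only, 32 GPs and 192 patients per arm, district ICC 0.01-0.05, GP ICC 0.02-0.05. The components are s_d = 0.25 × ICC_d, s_g = 0.25 × ICC_g and s_e = 0.25 − s_d − s_g.

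*Chance difference between two sets of three districts*, SD = √(2·s_d/3):
- ICC_d 0.01: √(2 × 0.0025/3) = 4.1 points.
- ICC_d 0.05: √(2 × 0.0125/3) = 9.1 points.

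*Districts as the unit*, variance 2(s_d/3 + s_g/32 + s_e/192), t on 4 df = 2.776:
- ICC_d 0.01, ICC_g 0.02: 2(0.000833 + 0.000156 + 0.001263) = 0.004505; SE 6.71 points; half-width 18.6 points.
- ICC_d 0.05, ICC_g 0.05: 2(0.004167 + 0.000391 + 0.001172) = 0.011458; SE 10.70 points; half-width 29.7 points.

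*GPs randomised within districts*, variance 2(s_g/32 + s_e/192), t on 64 − 6 − 1 = 57 df = 2.002:
- Narrowest (ICC_d 0.05, ICC_g 0.02): 2(0.000156 + 0.001211) = 0.002734; SE 5.23 points; half-width 10.5 points.
- Widest (ICC_d 0.01, ICC_g 0.05): 2(0.000391 + 0.001224) = 0.003229; SE 5.68 points; half-width 11.4 points.

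Power for a 15-point difference (an illustrative value, not in the protocol) is 19-40% with districts as the unit and 74-81% with GPs within districts. The second set of figures assumes no leakage between practices and an equal effect in every district.

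**The case against.** **The wording may describe one cluster scheme, badly.** The table could be the list of districts, with each patient entering by district. That is possible. The natural reading of patients being randomised by an entry table is still a list of patients, and nothing in the document corrects it. The need to reconcile the sentences stands.

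**The named sets may be the result of a draw.** A reader might infer that only one coin toss separates the arms, and that a randomisation test could then never give a two-sided p below 1.0. The protocol does not establish this. An unreported draw of 3 of 6 districts would be one of 20 outcomes, so the inference must stay conditional. Moreover, section 8.3 plans no randomisation test. Even a proper 3-versus-3 draw would have a smallest two-sided p of 2/20 = 0.10 under such a test, whereas a district-level t test on 4 df can reach 0.05. The smallest p therefore does not decide the matter.

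**Baseline data and ANCOVA help.** A reader might also infer that no analysis could remove district differences. That goes too far. The Phase III data-collection text provides for measurement at the beginning and end (printed as Phase II), and section 8.3 permits ANCOVA. A stable difference in level would largely show at baseline and could be adjusted for. Unmeasured differences and different change over six months remain, and the adjustment is optional.

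**Whole districts limit leakage.** Leaflets and GP talks can pass between neighbouring colleagues, so randomising GPs within a district has a price that the figures above leave out. Using centres would reduce leakage, but the number of centres per district is not stated. If it is one, centres cannot be randomised within districts. This objection stands in full.

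**Conclusion.** The point holds in this form. Section 4 states the Phase III allocation in ways that do not fit together on their natural reading, and no other section resolves them. Wherever the named groups are kept, three whole districts form each arm and lasting differences between the sets are confounded with the intervention. Baseline adjustment would reduce this only partly and by assumption. Unless a random 3-of-6 draw produced the sets, at most one toss between two preset sets remains and 'randomised' is weakly supported.

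The contradiction and the count of 20 against 2 need no assumption about variance. The half-widths (about 19-30 points against about 11) and the chance difference between sets (SD 4.1-9.1 points) rest on assumed ICCs, a binary outcome near 50% and end-only data. They show an order of size and are not estimates for this trial. The documents do not show that the trial must move to GP-level randomisation.

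**What to change.** Before Phase III starts, amend section 4 as follows:

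1. State one unit of allocation and one rule.
2. If districts carry the arm, delete the wording on the patient entry table.
3. Replace the pre-named sets with a documented random draw of 3 of the 6 districts, or report the draw that produced them. State which set is exposed.
4. Describe and interpret Phase III as a six-cluster comparison. If no draw is made, describe it as a non-randomised comparison of two district groups.

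This costs protocol wording and one draw, and no extra patients. It does not narrow the interval: six districts remain six clusters.

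As an option, centres or GPs could be randomised 1:1 within each district, with all patients of a unit taking its arm. That balances district differences by design. The costs are delivery of the intervention in all six districts and possible leakage between practices. The sponsor must first establish how many centres each district has. The half-width of about 11 points was worked out for 64 separately randomised GPs and does not carry over to centres.
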